
In designing a treatment that can be employed by PC-MHI providers, we considered several options but ultimately chose to modify the VA's full length CBT protocol³². First, CBT has the most well-established evidence base of psychotherapies for chronic pain^{31,33} and has therefore been rolled out extensively in VA. Second, a recent trial comparing CBT to another form of therapy for chronic pain, mindfulness-based stress reduction, found that the effect of these treatments is equivalent³⁴, indicating that mindfulness does not offer significant advantages over CBT. Third, six-session CBT for chronic pain groups have been shown to be cost effective for use in non-VA primary care³⁵, suggesting the potential of a briefer version of CBT in the primary care setting. Fourth, our prior work has shown that a clear majority of PC-MHI providers self-report use of CBT techniques as part of their routine practice to address other mental health conditions³⁶⁻³⁹. Nationally, some PCMHI providers play a role in delivering psychoeducational group interventions, or "pain schools", in primary care, yet the availability of these interventions is variable and the content is not standardized. Significantly, their overall effectiveness at improving patient outcomes appears marginal⁴⁰, suggesting that pain schools may be insufficient as the principal approach to addressing the psychosocial aspects of chronic pain. Therefore, a standardized protocol would capitalize on therapeutic elements that have demonstrated effectiveness, match well with the PC-MHI treatment platform, and address a significant concern among primary care patients.

Significance

The long term goal of this research is to promote recovery and psychological wellness among Veterans with chronic pain. The proposed study will advance knowledge in rehabilitation research by providing preliminary data regarding the feasibility and effectiveness of Brief CBT-CP as a front line treatment. More immediately, this pilot study will provide the necessary information to develop a proposal for a full scale effectiveness trial. This intervention has been designed specifically for PC-MHI providers and therefore has clear implications for translation to clinical practice. The potential direct benefit to Veterans includes offering a safe, accessible, evidence-based, non-pharmacological treatment for chronic pain early in the trajectory of VA care.

Research Design and Methods

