Conceptual framework. The biopsychosocial model of pain⁴¹ suggests that unchecked chronic pain can negatively impact activity engagement out of fear associated with movement. Limiting one's beneficial activities can result in physical deconditioning and avoidance of pleasurable events. Persistent pain and disengagement can lead to emotional distress and decreased motivation that result in further social/occupational role withdrawal. The subsequent state of disability is reinforced by maladaptive coping. Brief CBT-CP is aligned with this model and designed to target the biological (e.g., relaxation training), psychological (e.g., cognitive coping), and social (e.g., decreasing isolation) aspects of pain to improve long-term health outcomes. **Design** considerations and overview. This aim will evaluate the feasibility of Brief CBT-CP via a pilot randomized controlled trial (RCT). We will focus on feasibility outcomes because Brief CBT-CP has not been subject to prior research and documentation of the viability of study processes will provide critical information for future effectiveness studies⁴². We chose to randomize participants in order to have a realistic assessment of the stratified randomization procedure, retention of control participants, and assessment of the impact of our control condition on patient outcomes⁴³. Primary care treatment as usual (TAU) was chosen because the long term goal of developing Brief CBT-CP is to improve upon usual care practices of PACTs by adding a behavioral protocol for PC-MHI providers. We considered but excluded the use of a pain psychoeducation condition because this approach would not reflect true usual care practices at our study site (and many other VA primary care clinics). A psychoeducation control would need to be developed specifically for this trial and its use is not as well suited to our study question about whether Brief CBT-CP improves upon primary care TAU. A psychoeducation control is better suited to answering the question about the impact of specific CBT components above the impact of education and supportive contacts with a therapist.⁴⁴ Similarly, use of primary care TAU will best serve the goal of conducting a future effectiveness trial in real world primary care. 45 **Participants.** We will recruit 30 Veterans from the primary care clinics located at the Buffalo VAMC in Buffalo. NY. Thirty eligible participants will be randomized in a 1:1 ratio into either (1) Brief CBT-CP plus TAU or (2) TAU only. We will engage in recruitment during the second guarter of Year 1 through the end of the first quarter of Year 2. We aim to recruit and enroll 7-8 participants per quarter (or 2-3 patients per month) during that time frame. Post-treatment follow-up will be conducted at eight weeks and at 12 weeks.

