Patients will be excluded if chart review indicates either of the following: 1) unstable psychiatric status (e.g., active psychosis, current mania) or 2) major or minor neurocognitive disorder (e.g., dementia). Patients will also be excluded if chart review reveals uncontrolled medical conditions, scheduled/planned surgeries, and medical or other interventions likely to impact pain/functional ratings. Potential participants will not be excluded based on past/current/future use of chiropractic care or physical therapy.

Procedures. As shown in Figure 1, upon completing baseline measures, eligible participants will be randomly assigned to (1) Brief CBT-CP plus TAU or (2) TAU only. Assignment to Brief CBT-CP will be stratified based on degree of pain interference as measured by West Haven-Yale Multidimensional Pain Inventory – Interference (WHYMPI-I)⁵³. Participants will be classified as average interference and below (WHYMPI-I score ≤ 4.4) or as above average interference (WHYMPI-I score >4.4)^{28,53}. All participants will complete a telephone-based follow-up with the study coordinator, who will be blinded to participants' condition, at 8 weeks (post-test) and at 12 weeks (follow-up) from randomization for re-administration of study measures. Participants will be compensated \$40 for the initial assessment and \$30 for each of two follow ups (total \$100 for Aim 1). We will replace dropouts who do not meet minimum treatment completion requirements of attending ≥ 4 sessions. Attending, at minimum, sessions one through four will provide patients with essential education and core CBT self-management skills. Although some dropout is planned, we predict that we will replace only a small number of participants (~3-4) prior to our final 12-week follow-up assessment. This prediction is informed by [name] (Co-I) current clinical trial (IIR I01HX000909) of a brief behavioral intervention for depression conducted at the Buffalo VAMC primary care clinics which used similar methodology. At 90% completion, this study has evidenced only 11.3% participant drop out at 12-week follow-up.

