TAU only: Participants assigned to TAU only will receive standard medical care from their primary care provider including pain medications, brief advice (e.g., use of relative rest, application of heat or ice, other selfcare strategies), or referral to pain-related adjunctive interventions (e.g., physical therapy), as indicated. Participants in TAU only will not receive behavioral intervention from the primary care clinic PC-MHI provider. **Aim 1 Analysis plan.**

Sample size: We will recruit and randomize 30 participants (approximately 2-3 participants per month for 12 months). Based on prior research in these clinics, we estimate that about 225 unique patients per month will report for primary care with a chronic musculoskeletal diagnosis. Previous work by our team indicates that this figure is highly feasible.

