Exploratory analysis of patient outcomes: Means, standard deviations, and confidence intervals (CIs) at each of the three measurement times per condition will be calculated. We will also generate a preliminary effect size at post-treatment and follow-up based on the WHYMPI – I. Effect sizes will be calculated by dividing the mean difference between intervention and control conditions by the pooled standard deviation. Then, 95% CIs will be calculated on the effect size by using the non-central *t*-distribution method⁶³. While this study is not adequately powered to detect small changes in patient outcomes, the mean WHYMPI-I score in each condition at post treatment will be compared (while adjusting for the baseline score) using analysis of co-variance (ANCOVA). Adjusting for baseline pain interference reduces the residual variance of the ANCOVA model thereby increasing power, and attributes potential differences between conditions at post treatment to the condition, not the baseline score (regression to the mean). Stratifying the randomization scheme according to baseline pain interference will also decrease the likelihood of regression to the mean, and using ANCOVA minimizes its effect at post treatment⁶⁴. A similar analysis will be conducted at follow-up and will be repeated with the remaining patient outcome measures. As an alternative to ANOCVA, we will also explore the use of multi-level modeling approaches. Multiple imputation will be used for any missing data⁶⁵. **Risks and data security** Potential Risks

Across study aims, one possible risk to participants is that of potential disclosure of sensitive information. Several steps will be taken to minimize risk of breaching confidentiality including educating research staff about confidentiality and ethical issues in regard to the study. All electronic and paper self-report data collected will be identified by a unique study identification number rather than individually identifiable information. Identifiable voice recordings will be stored separately and in accordance with the data security and privacy procedures below. Identifiable information for informed consent, payment, and enrollment status will be stored separately from study data and will also comply with the data security and privacy procedures. Data security and privacy procedures (below) are designed to minimize this risk.

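### The preliminary WHYMPI-I effect size carries no small-sample correction and is on average about 3% too far from zero; reporting Hedges' g removes this at no cost

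*Combined protocol and SAP*

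**What the plan says.** In the Aim 1 Analysis plan, under Exploratory analysis of patient outcomes, the plan commits to an effect size at two time points: "We will also generate a preliminary effect size at post-treatment and follow-up based on the WHYMPI" interference subscale, its primary patient outcome. The estimator is fully specified: "Effect sizes will be calculated by dividing the mean difference between intervention and control conditions by the pooled standard deviation". The interval is also named: "95% CIs will be calculated on the effect size by using the non-central" t-distribution method. No bias correction for the point estimate appears anywhere in the document.

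The size is fixed under Sample size ("We will recruit and randomize 30 participants") and Participants ("Thirty eligible participants will be randomized in a 1:1 ratio"). Two statements under Procedures bear on how many will be analysed. One concerns a similar trial at the site: "this study has evidenced only 11.3% participant drop out at 12-week follow-up". The other concerns replacement: "we predict that we will replace only a small number of participants (~3-4) prior to our final 12-week follow-up assessment". Missing data are to be multiply imputed.

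On later use, the Significance section says that "this pilot study will provide the necessary information to develop a proposal for a full scale effectiveness trial". It does not say that the effect size will set that trial's sample size.

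**The concern.** The sample pooled standard deviation stands in the denominator. The average of its reciprocal exceeds the reciprocal of the true standard deviation, so the ratio is on average too far from zero. In a large trial this is negligible. With about 28 degrees of freedom it is still small, but it is known exactly and can be removed exactly. The plan already uses an exact method for the interval, so pairing that interval with an uncorrected point estimate is an avoidable inconsistency.

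At stake is the single standardised effect that the pilot will report. If a later proposal took it at face value, the required sample size would inherit the error roughly doubled, because sample size varies with one over the effect squared.

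**Working it through.** **The plan's own figure.** The documents give no target effect, standard deviation, alpha or power, so there is no power-based sample size to reproduce. The 30 agrees with the accrual figures: 2-3 per month × 12 months = 24-36, and 7-8 per quarter × 4 quarters = 28-32.

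**Inputs from the documents.** 30 randomised 1:1, so 15 per arm and df = 30 - 2 = 28. With 11.3% loss and no replacement, 30 × 0.887 = 26.6, so 26 or 27 analysed. With 3-4 replacements, 33-34 are randomised; if all are analysed, df is 31 or 32.

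**Formulas.** Write d for the plain ratio and δ for the true standardised effect. Under normality, E[d] = δ / J(df), with

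J(df) = Γ(df/2) / [√(df/2) × Γ((df-1)/2)] ≈ 1 - 3/(4·df - 1).

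At df = 28 the approximation gives 1 - 3/111 = 0.973; the exact value is 0.9729. The average overstatement is 1/J - 1. Because n is proportional to 1/d², a sample size computed from E[d] is short by 1 - J², and restoring it needs 1/J² - 1 more.

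| Analysed | df | J | Overstatement | Later N too small by | Extra needed |
|---|---|---|---|---|---|
| 34 | 32 | 0.9763 | 2.4% | 4.7% | 4.9% |
| 33 | 31 | 0.9756 | 2.5% | 4.8% | 5.1% |
| 30 | 28 | 0.9729 | 2.8% | 5.3% | 5.6% |
| 27 | 25 | 0.9696 | 3.1% | 6.0% | 6.4% |
| 26 | 24 | 0.9684 | 3.3% | 6.2% | 6.6% |

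**What the shortfall would mean.** Assume δ = 0.5, 80% power and two-sided alpha 0.05 (none of these is in the documents). The full-scale trial needs 63 per arm. Using E[d] gives 60 per arm from a pilot of 30, or 59 from a pilot of 26. Power at those sizes is about 78.2% and 77.5% instead of 80%.

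**How it compares with chance.** At δ = 0.5 and 15 per arm, E[d] = 0.5/0.9729 = 0.514, a bias of 0.014. The standard deviation of d is about 0.386, so the bias is 0.014/0.386, or about 4% of one standard error. The non-central t 95% interval at an observed d of 0.5 is -0.23 to 1.22. It is an interval for the true standardised effect, so it does not carry the bias.

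**Does the correction help a single estimate?** At δ = 0.5, the mean squared error of d is 0.386² + 0.014² = 0.149. The corrected value has no bias and a standard deviation of 0.9729 × 0.386 = 0.3755, so its mean squared error is 0.141. Simulation at 15 per arm with assumed true effects of 0.2, 0.5 and 0.8 gave lower mean squared error and lower median absolute error for the corrected value each time.

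**Adjusted or raw difference.** The plan does not say whether the numerator is baseline-adjusted. It makes little difference, since the bias comes from the denominator. Simulation with 15 per arm, δ = 0.5 and an assumed baseline correlation of 0.6 gave 2.7% for both.

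**The case against.** The strongest reply is that this is a choice of convention in an exploratory analysis. The plan puts feasibility first, calls the effect size preliminary, concedes limited power for small changes and already reports an interval that shows how little the point estimate settles. Anyone given the means, standard deviations and group sizes can apply the correction later. All of this stands, and it is why the point ranks as a free improvement only.

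A sharper version is that plain d is nearly right in the median: at 15 per arm and δ = 0.5 its median is only 0.9% high and it exceeds the truth 50.5% of the time, whereas the corrected value has a median about 1.8% low. Those figures are right, but they do not show that d is usually closer to the truth. On both mean squared error and median absolute error the corrected value did better.

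Four stronger readings are tempting and are not supported:

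- A reader might infer that the full-scale trial will be undersized. The documents say that the pilot informs a proposal, not that this estimate sets its sample size. The use of pilot figures that the plan does describe is refusal and recruitment rates, to estimate how many must be screened.
- A reader might infer that the estimate is always optimistic. The bias is in the average and away from zero: nil with no effect, and exaggerating harm if the effect is adverse. Any one pilot estimate may be too low.
- A reader might take 28 as the most degrees of freedom possible. The replacement rule can raise it to about 32.
- A reader might extend the range to 7% by supposing that only 24 are analysed. The only dropout figure given is 11.3%.

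**Conclusion.** The point holds as a minor reporting matter. The estimator as written is biased away from zero in expectation, in proportion to the true effect: about 2.8% with 30 analysed, 3.1-3.3% with 26-27, and about 2.4% with 34. A later sample size based on its expected value would be about 5-6% too small, but only if the estimate were carried forward, which the plan does not state.

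The percentages for bias assume normal outcomes with a common variance and df equal to the number analysed minus 2. Under multiple imputation the effective df is not exactly that, so J is then approximate. The sampling error of d is more than 25 times the bias at δ = 0.5 (0.386/0.014), so imprecision remains by far the larger hazard in planning from this pilot.

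**What to change.** Add one sentence to Exploratory analysis of patient outcomes: each effect size, at post-treatment and at follow-up, will be multiplied by the exact factor J(df), with df taken from the participants actually analysed at that time point, and reported as Hedges' g. Note that the factor is approximate where multiple imputation is used. Keep the non-central t 95% interval as planned.

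The cost is that sentence and one line of code. No data, participants or design features change, and the reported effect becomes about 3% smaller.

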during follow-up assessment calls. To assess the suitability of our measures of patient outcome measures, we will examine item response rates, including the number of missed responses and multiple responses, and time required for completion. We will also document any questions or comments raised by the participant during measure administration. To assess fidelity of service delivery, the study interventionist will complete an adherence checklist after each session. Checklists map on to each of the six sessions of Brief CBT-CP and will be designed to capture key content and procedures. All intervention sessions will be audio recorded with the participant's permission. The PI will randomly select 25% of the audio recordings for review by [name] (study Co-I) using an adapted version of the CBT-CP Rating Scale⁵⁵. To examine the precise nature of participants' service utilization during the trial, we will conduct a chart review at 12-week follow-up. Chart review will assess participants' engagement in primary medical care (i.e., PACT encounters), PC-MHI encounters, and other VA services to assist with assessing feasibility of TAU only as a control condition and will assess any changes in pain or psychotropic medication initiated since baseline assessment. Aim 1 Measures of patient outcomes. Patient outcome measures will be assessed at baseline, post treatment (eight weeks), and follow-up (12 weeks). Administration of all study measures will take about one hour at each time point.

- West Haven-Yale Multidimensional Pain Inventory Interference (WHYMPI-I). The WHYMPI-I is a validated 9-item subscale that evaluates pain-related interference in daily activities and social and occupational functioning⁵³. It is among the core assessments included in the full-length CBT for Chronic Pain³² and is the primary patient outcome for this trial.
- Brief Pain Inventory Short Form (BPI-SF): The BPI-SF is a psychometrically validated 9-item measure that assesses pain level (current and average), pain related functional impairment, and activity interference. The BPI-SF asks participants to indicate the extent of their pain as well as any interference with various activities and other aspects of life (i.e., mood, relationships) using a scale ranging from 0 (no pain/interference) to 10 (worst pain/complete interference). This measure is included in order to further assess pain outcomes in response to Brief CBT-CP.

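### The plan names no stratification covariate for the ANCOVAs of the seven patient outcomes other than WHYMPI-I; adding baseline WHYMPI-I would be a small, free gain in precision

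*Combined protocol and SAP*

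**What the plan says.** Procedures: "Assignment to Brief CBT-CP will be stratified based on degree of pain interference as measured by West Haven-Yale Multidimensional Pain Inventory" Interference, with two strata divided at a score of 4.4. The score is available for everyone randomised, because "upon completing baseline measures, eligible participants will be randomly assigned to (1) Brief CBT-CP plus TAU or (2) TAU only".

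Participants: "Thirty eligible participants will be randomized in a 1:1 ratio into either (1) Brief CBT-CP plus TAU or (2) TAU only".

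Exploratory analysis of patient outcomes: post-treatment WHYMPI-I is compared between conditions by ANCOVA with its baseline value as covariate. The stated reasons are lower residual variance, more power and control of regression to the mean. The plan then says: "A similar analysis will be conducted at follow-up and will be repeated with the remaining patient outcome measures". It adds that multi-level models will be explored as an alternative. No covariate list is given for the other outcomes or for the multi-level models.

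**The concern.** When allocation is balanced within strata of a prognostic variable, the treatment estimate varies less from trial to trial than it would under simple randomisation. A model without that variable does not credit the reduction: the variance it explains stays in the error term, so the standard error is too large for the design actually used. Adjusting for the variable also removes chance imbalance that remains within strata.

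The WHYMPI-I model is not affected, because its baseline covariate is the continuous form of the stratification variable. The question concerns the other seven measures, each at 8 and 12 weeks (7 x 2 = 14 comparisons). At stake is some interval width in a study that says it lacks power for small changes and that is meant to inform a full-scale trial proposal. The plan's own argument for adjustment, less residual variance and more power, would apply to these models too.

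**Working it through.** **Figure in the plan.** The sample size of 30 rests on accrual, not power. Participants gives 7-8 per quarter over four quarters: 7 x 4 = 28 to 8 x 4 = 32. Sample size gives 2-3 per month over 12 months: 2 x 12 = 24 to 3 x 12 = 36. Both are consistent with 30. No effect size, SD or power target is stated, so there is no power figure to reproduce.

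**Inputs from the documents.** n = 30, 1:1 allocation, two strata of baseline WHYMPI-I, baseline measured before assignment, 95% intervals.

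**Assumptions, not in the documents.** Permuted blocks of 4; strata split 50/50; correlation 0.6 between an outcome and its own baseline; correlation 0.4 between that baseline and baseline WHYMPI-I; complete data; two-sided 5% tests. The key unknown is the partial correlation r between the outcome and baseline WHYMPI-I given the outcome's own baseline, set to 0, 0.2, 0.3 and 0.5.

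**Method.** 20,000 simulated trials per scenario, each analysed by three ANCOVAs: own baseline only; own baseline plus stratum; own baseline plus continuous baseline WHYMPI-I.

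Mean 95% CI width in outcome SDs (no true effect), with change from own baseline only:

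| r | Own baseline only | + stratum | + continuous WHYMPI-I |
|---|---|---|---|
| 0 | 1.209 | 1.215 (+0.5%) | 1.223 (+1.2%) |
| 0.2 | 1.208 | 1.199 (-0.7%) | 1.196 (-1.0%) |
| 0.3 | 1.209 | 1.181 (-2.3%) | 1.165 (-3.6%) |
| 0.5 | 1.211 | 1.119 (-7.6%) | 1.057 (-12.7%) |

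Check by formula: the width ratio should be about sqrt(1 - r²) times the cost of one more covariate, which the r = 0 row puts at 1.223/1.209 = 1.012.
- r = 0.2: 0.980 x 1.012 = 0.991
- r = 0.3: 0.954 x 1.012 = 0.965
- r = 0.5: 0.866 x 1.012 = 0.876

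The simulated ratios are 0.990, 0.964 and 0.873, in agreement.

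Two-sided type I error, and power for an assumed 0.8 SD effect (own baseline only / + stratum / + continuous):

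| r | Type I error | Power |
|---|---|---|
| 0 | 5.2 / 5.2 / 5.2% | 73 / 73 / 73% |
| 0.2 | 4.7 / 4.9 / 4.9% | 74 / 74 / 75% |
| 0.3 | 4.7 / 5.1 / 5.1% | 74 / 76 / 77% |
| 0.5 | 3.8 / 4.9 / 5.0% | 76 / 81 / 84% |

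The Monte Carlo standard error of a 5% rate is sqrt(0.05 x 0.95/20,000) = 0.15 percentage points. So 4.7% is about two standard errors below nominal, and 3.8% is clearly below it. Mean error of the estimate is at most 0.003 SD in every model and scenario, so there is no bias.

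Not all of the narrowing is new precision. At r = 0.5 the actual SD of the estimate falls from 0.278 to 0.260, a ratio of 0.935, or about 6%. The rest of the 13% is the interval ceasing to be too wide for the design. At r = 0.3 the SD falls from 0.290 to 0.285 (about 2%), and at r = 0.2 it stays at 0.294.

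**The case against.** The strongest objection is that the omission is inferred. The plan never writes that the other outcomes are adjusted for their own baseline and nothing else. Its rationale names baseline pain interference as the adjusting variable and then links it to the stratified randomisation, so a similar analysis could mean baseline WHYMPI-I in every model. Own-baseline adjustment is the more natural reading, but the other cannot be fully excluded. What stands is that the covariates are not listed. Listing them settles either reading, including the one in which the outcome's own baseline would be missing.

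Second, the gain depends on a quantity that the documents do not give, and it may lie at the low end. The BPI-SF itself measures interference, so its baseline may already carry much of the WHYMPI-I information. Screening requires a score of at least 4 on a PEG interference item, which may narrow the range of baseline interference. At r = 0.2 the gain is about 1%, and at r = 0 there is a loss of about 1%. This stands: the 13% figure is the far end of an assumed range, not a typical value.

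Third, no planned decision rests on these models. The primary outcomes are feasibility measures analysed descriptively, and the only effect size the plan commits to is for WHYMPI-I, which is untouched. This also stands and limits the weight of the point.

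**Conclusion.** The point holds as a minor one. Seven exploratory ANCOVAs have no stated stratification covariate, although the variable is measured in everyone before randomisation. For partial correlations from 0 to 0.5, continuous baseline WHYMPI-I would change interval width by between +1% and -13%; the stratum indicator would change it by between +0.5% and about -8%. These sizes rest on the assumed correlations, blocks of 4, a 50/50 stratum split and complete data at n = 30.

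A reader might infer more than the documents support:
- That the comparisons are biased or too liberal. They are not: the estimates are unbiased, and where r is above 0 the error is towards conservatism (type I error 3.8-4.7%).
- That the plan expressly excludes the stratification variable. It is silent.
- That every outcome is affected. WHYMPI-I is covered by its own baseline. The WAI-SR asks about the therapist, so no ordinary baseline-adjusted comparison between arms is available for it.
- That the multiple imputation shares the fault. Nothing in this check tests that.

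**What to change.** In Exploratory analysis of patient outcomes, list the covariates. For BPI-SF, PHQ-9, GAD-7, PSEQ, PCS, WHOQOL-BREF and APSRA, at 8 and at 12 weeks, state that the ANCOVA and any multi-level alternative include condition, the measure's own baseline, and baseline WHYMPI-I. Either the continuous score or the stratum indicator will do. The continuous score gains as much or more when r is above 0, and the two differ little at r = 0.2. Choose one form before the outcome data are seen and use it throughout.

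The cost is one sentence and one residual degree of freedom (30 - 3 = 27 becomes 30 - 4 = 26). If baseline WHYMPI-I adds nothing, intervals widen by about 1%. No new data are needed and no trial procedure changes.
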